7.2.3.2 Events of Clinical Interest

Selected non-serious and serious adverse events are also known as Events of Clinical Interest (ECI) and must be reported to the Sponsor.

For the time period beginning when the consent form is signed until treatment allocation/randomization, any ECI, or follow up to an ECI, that occurs to any subject must be

reported within 24 hours to the Sponsor if it causes the subject to be excluded from the trial, or is the result of a protocol-specified intervention, including but not limited to washout or discontinuation of usual therapy, diet, placebo treatment or a procedure.

For the time period beginning at treatment allocation/randomization through 30 days following cessation of treatment, any ECI, or follow up to an ECI, whether or not related to the Sponsor's product, must be reported within 24 hours to the Sponsor, either by electronic media or paper. Electronic reporting procedures can be found in the EDC data entry guidelines. Paper reporting procedures can be found in the Investigator Trial File Binder (or equivalent).

Events of clinical interest for this trial include:

1. an overdose of Sponsor's product, as defined in Section 7.2.1 - Definition of an Overdose for This Protocol and Reporting of Overdose to the Sponsor, that is not associated with clinical symptoms or abnormal laboratory results.
2. an elevated AST or ALT lab value that is greater than or equal to 3X the upper limit of normal and an elevated total bilirubin lab value that is greater than or equal to 2X the upper limit of normal and, at the same time, an alkaline phosphatase lab value that is less than 2X the upper limit of normal, as determined by way of protocol-specified laboratory testing or unscheduled laboratory testing.*

***Note:** These criteria are based upon available regulatory guidance documents. The purpose of the criteria is to specify a threshold of abnormal hepatic tests that must trigger an additional evaluation for an underlying etiology. The trial site guidance for assessment and follow up of these criteria can be found in the Investigator Trial File Binder (or equivalent).

It may also be appropriate to conduct additional evaluation for an underlying etiology in the setting of abnormalities of liver blood tests including AST, ALT, bilirubin, and alkaline phosphatase that do not meet the criteria noted above. In these cases, the decision to proceed with additional evaluation will be made through consultation between the study investigators and the Sponsor Clinical Director. However, abnormalities of liver blood tests that do not meet the criteria noted above are not ECIs for this trial.

7.2.4 Evaluating Adverse Events

An investigator who is a qualified physician will evaluate all adverse events according to the NCI Common Terminology for Adverse Events (CTCAE), version 4.0. Any adverse event which changes CTCAE grade over the course of a given episode will have each change of grade recorded on the adverse event case report forms/worksheets.

All adverse events regardless of CTCAE grade must also be evaluated for seriousness.

Table 4 Evaluating Adverse Events

An investigator who is a qualified physician, will evaluate all adverse events as to:

V4.0 CTCAE Grading	Grade 1	Mild; asymptomatic or mild symptoms; clinical or diagnostic observations only; intervention not indicated.
	Grade 2	Moderate; minimal, local or noninvasive intervention indicated; limiting age-appropriate instrumental ADL.
	Grade 3	Severe or medically significant but not immediately life-threatening; hospitalization or prolongation of hospitalization indicated; disabling; limiting self-care ADL.
	Grade 4	Life threatening consequences; urgent intervention indicated.
	Grade 5	Death related to AE
Seriousness	A serious adverse event is any adverse event occurring at any dose or during any use of Sponsor's product that:	
	† Results in death ; or	
	† Is life threatening ; or places the subject, in the view of the investigator, at immediate risk of death from the event as it occurred (Note: This does not include an adverse event that, had it occurred in a more severe form, might have caused death.); or	
	† Results in a persistent or significant disability/incapacity (substantial disruption of one's ability to conduct normal life functions); or	
	† Results in or prolongs an existing inpatient hospitalization (hospitalization is defined as an inpatient admission, regardless of length of stay, even if the hospitalization is a precautionary measure for continued observation. (Note: Hospitalization for an elective procedure to treat a pre-existing condition that has not worsened is not a serious adverse event. A pre-existing condition is a clinical condition that is diagnosed prior to the use of a Merck product and is documented in the patient's medical history.); or	
	† Is a congenital anomaly/birth defect (in offspring of subject taking the product regardless of time to diagnosis); or	
	Is a new cancer (that is not a condition of the study) (although not serious per ICH definition, is reportable to the Sponsor within 24 hours to meet certain local requirements); or	
	Is an overdose (whether accidental or intentional). Any adverse event associated with an overdose is considered a serious adverse event for collection purposes. An overdose that is not associated with an adverse event is considered a non-serious event of clinical interest and must be reported within 24 hours.	
	Other important medical events that may not result in death, not be life threatening, or not require hospitalization may be considered a serious adverse event when, based upon appropriate medical judgment, the event may jeopardize the subject and may require medical or surgical intervention to prevent one of the outcomes listed previously (designated above by a †).	
Duration	Record the start and stop dates of the adverse event. If less than 1 day, indicate the appropriate length of time and units	
Action taken	Did the adverse event cause the Sponsor's product to be discontinued?	
Relationship to Sponsor's Product	Did the Sponsor's product cause the adverse event? The determination of the likelihood that the Sponsor's product caused the adverse event will be provided by an investigator who is a qualified physician. The investigator's signed/dated initials on the source document or worksheet that supports the causality noted on the AE form, ensures that a medically qualified assessment of causality was done. This initialed document must be retained for the required regulatory time frame. The criteria below are intended as reference guidelines to assist the investigator in assessing the likelihood of a relationship between the test drug and the adverse event based upon the available information. The following components are to be used to assess the relationship between the Sponsor's product and the AE; the greater the correlation with the components and their respective elements (in number and/or intensity), the more likely the Sponsor's product caused the adverse event (AE):	
Exposure	Is there evidence that the subject was actually exposed to the Sponsor's product such as: reliable history, acceptable compliance assessment (pill count, diary, etc.), expected pharmacologic effect, or measurement of drug/metabolite in bodily specimen?	
Time Course	Did the AE follow in a reasonable temporal sequence from administration of the Sponsor's product? Is the time of onset of the AE compatible with a drug-induced effect (applies to trials with investigational medicinal product)?	
Likely Cause	Is the AE not reasonably explained by another etiology such as underlying disease, other drug(s)/vaccine(s), or other host or environmental factors	

Relationship to Sponsor's Product (continued)	The following components are to be used to assess the relationship between the test drug and the AE: (continued)	
	Dechallenge	Was the Sponsor's product discontinued or dose/exposure/frequency reduced? If yes, did the AE resolve or improve? If yes, this is a positive dechallenge. If no, this is a negative dechallenge. (Note: This criterion is not applicable if: (1) the AE resulted in death or permanent disability; (2) the AE resolved/improved despite continuation of the Sponsor's product; or (3) the trial is a single-dose drug trial); or (4) Sponsor's product(s) is/are only used one time.)
	Rechallenge	Was the subject re-exposed to the Sponsor's product in this study? If yes, did the AE recur or worsen? If yes, this is a positive rechallenge. If no, this is a negative rechallenge. (Note: This criterion is not applicable if: (1) the initial AE resulted in death or permanent disability, or (2) the trial is a single-dose drug trial); or (3) Sponsor's product(s) is/are used only one time). NOTE: IF A RECHALLENGE IS PLANNED FOR AN ADVERSE EVENT WHICH WAS SERIOUS AND WHICH MAY HAVE BEEN CAUSED BY THE SPONSOR'S PRODUCT, OR IF REEXPOSURE TO THE SPONSOR'S PRODUCT POSES ADDITIONAL POTENTIAL SIGNIFICANT RISK TO THE SUBJECT, THEN THE RECHALLENGE MUST BE APPROVED IN ADVANCE BY THE SPONSOR CLINICAL DIRECTOR AS PER DOSE MODIFICATION GUIDELINES IN THE PROTOCOL.
Consistency with Trial Treatment Profile		Is the clinical/pathological presentation of the AE consistent with previous knowledge regarding the Sponsor's product or drug class pharmacology or toxicology?
The assessment of relationship will be reported on the case report forms /worksheets by an investigator who is a qualified physician according to his/her best clinical judgment, including consideration of the above elements.		
Record one of the following		Use the following scale of criteria as guidance (not all criteria must be present to be indicative of a Sponsor's product relationship).
Yes, there is a reasonable possibility of Sponsor's product relationship.		There is evidence of exposure to the Sponsor's product. The temporal sequence of the AE onset relative to the administration of the Sponsor's product is reasonable. The AE is more likely explained by the Sponsor's product than by another cause.
No, there is not a reasonable possibility of Sponsor's product relationship		Subject did not receive the Sponsor's product OR temporal sequence of the AE onset relative to administration of the Sponsor's product is not reasonable OR the AE is more likely explained by another cause than the Sponsor's product. (Also entered for a subject with overdose without an associated AE.)

7.2.5 Sponsor Responsibility for Reporting Adverse Events

All Adverse Events will be reported to regulatory authorities, IRB/IECs and investigators in accordance with all applicable global laws and regulations, i.e., per ICH Topic E6 (R1) Guidelines for Good Clinical Practice.

8.0 STATISTICAL ANALYSIS PLAN

The statistical analysis of the data obtained from this study will be conducted by, or under the direct auspices of Early Development Statistics – Asia Pacific (EDS-AP), in collaboration with the Pharmacokinetics, Pharmacodynamics & Drug Metabolism, Clinical Pharmacology /China Clinical Research Departments of the Sponsor.

If, after the study has begun, changes are made to the statistical analysis plan stated below, then these deviations to the plan will be listed, along with an explanation as to why they occurred, in the Clinical Study Report (CSR).

8.1 Statistical Analysis Plan Summary

This section contains a brief summary of the statistical analyses for this trial. Full detail is in the Statistical Analysis Plan (SAP) (Section 8.2).

Individual values will be listed for the PK parameters as shown below, and the following (non-model-based) descriptive statistics will also be provided: N (number of subjects with non-missing data), arithmetic mean, standard deviation, arithmetic percent CV (calculated as $100 \times \text{standard deviation}/\text{arithmetic mean}$), median, minimum, maximum, geometric mean, and geometric percent CV (calculated as $100 \times \text{sqrt}(\exp(s^2) - 1)$, where s^2 is the observed variance on the natural log-scale). On Day 10, the PK parameters are steady-state C_{avg} , AUC_{0-24hr} , C_{max} , C_{min} and T_{max} in subgroup 1. The frequency distribution with pre-specified exposure in two categories, <500 ng/mL and ≥ 500 ng/mL, for steady-state C_{avg} values on Day 10 in subgroup 1 will be tabulated. Descriptive statistics (mean and arithmetic percent CV) will also be tabulated for trough plasma concentrations in both subgroups by study day for MK-5592. In addition, mean trough plasma concentrations in both subgroups will be plotted by study day.

A population PK model was developed in non-Chinese healthy volunteer and patients to characterize PK and its variability after POS IV administration. Data from this study will be added to the dataset and the effect of Chinese ethnicity on the pharmacokinetics of posaconazole will be assessed. Also the percentage of the population with steady-state $C_{avg} \geq 500$ ng/mL will be estimated using the population PK model. Other necessary pharmacokinetic parameters will also be estimated from the population PK models.

8.2 Statistical Analysis Plan

8.2.1 Hypotheses/Estimation

The pharmacokinetics parameters (e.g., steady-state C_{avg} , AUC_{0-24hr}) of POS IV solution in Chinese subjects at high risk of invasive fungal infections will be estimated. Percentage of Chinese subjects with steady-state $C_{avg} \geq 500$ ng/ml will be estimated.

8.2.2 Analysis Endpoints

Primary key parameter for POS is steady-state C_{avg} . Other parameters (C_{min} , C_{max} , T_{max} , $AUC_{0-24\ hr}$ and CL) for POS IV administration will be determined from plasma samples taken at steady-state as described under Study Procedures.

For subgroup 1, blood samples for the determination of plasma trough POS levels will be drawn on Days 3, 6, 10 (± 1), 15 (± 1), 22 (± 1) and 28 (or EOT) for PK POS evaluation. Additional PK samples will be drawn on Day 10 (± 1) at pre-dose, 1 hour post start of infusion, immediately before the end of infusion, approximately 15 minutes after the end of infusion, and approximate 4, 8, 12 and 24 hours post start of infusion to further characterize additional PK parameters including $AUC_{0-24\ hr}$.

For subgroup 2, blood samples for the determination of plasma trough POS levels will be drawn on Days 3, 6, 10 (± 1), 15 (± 1), 22 (± 1) and 28 (or EOT) for PK POS evaluation.

Safety endpoints will include all types of adverse experiences, in addition to laboratory safety tests, ECGs, and vital signs. Efficacy endpoints including the percentage of IFI and survival assessment can be seen in Section 4.2.3.3.

8.2.3 Approaches to Analyses

The following populations are defined for the analysis and reporting of data. All subjects will be reported, and their data analyzed, according to the treatment(s) they actually received.

All Subjects as Treated (ASaT): All subjects who received at least one dose of the investigational drug. This population will be used for assessments of safety and tolerability.

Per-Protocol (PP) population: The set of data generated by the subset of subjects who comply with the protocol sufficiently to ensure that these data will be likely to exhibit the effects of treatment, according to the underlying scientific model. Compliance covers such considerations as exposure to treatment, availability of measurements and absence of major protocol deviations. Major protocol deviations will be identified to the extent possible prior to unblinding by individuals responsible for data collection/compliance, and its analysis and interpretation. Any subjects or data values excluded from analysis will be identified, along with their reason for exclusion, in the CSR. At the end of the study, all subjects who are compliant with the study procedure as aforementioned and have available data from at least one treatment will be included in the primary analysis dataset. This population will be used for the PK analysis.

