5.8 Subject Withdrawal/Discontinuation Criteria

Subjects may withdraw consent at any time for any reason or be dropped from the trial at the discretion of the investigator should any untoward effect occur. In addition, a subject may be withdrawn by the investigator or the Sponsor if enrollment into the trial is inappropriate, the trial plan is violated, or for administrative and/or other safety reasons. Specific details regarding discontinuation or withdrawal procedures; including specific details regarding withdrawal from Future Biomedical Research, are provided in Section 7.1.4 – Other Procedures.

Discontinuation from treatment is “permanent”. Once a subject is discontinued, he/she shall not be allowed to restart treatment.

A subject must be discontinued from the trial for any of the following reasons:

- The subject or legal representative (such as a parent or legal guardian) withdraws consent.
- Documentation of a fungal infection (proven, probable or possible IFI) according to the European Organization for Research and Treatment of Cancer/Invasive Fungal Infections and the National Institute of Allergy and Infectious Diseases Mycoses Study Group (EORTC-MSG version 2008) criteria [8];
- Subjects with a prolonged QTc interval on a manual measurement (QTc greater than 500 msec);
- A subject who, prior to start of study treatment and during study treatment, requires any of the prohibited medications listed in [Table 1](#) of Section 5.1.3.

- Inability to continue to take study medication according to schedule (See Section 5.2.2);
- Failure to comply with the dosing, evaluations, or other requirements of the study;
- A subject with liver function tests (ALT, AST, or total bilirubin) greater than 10 x ULN or other clinical or histopathologic evidence of drug-induced hepatotoxicity;
- A subject who has recovered from neutropenia ($ANC \geq 500/\text{mm}^3$) and has not considered risk factors of IFI remain at the discretion of investigator;
- The subject interrupts trial medication administration for more than 3 consecutive days;
- The subject has a medical condition or personal circumstance which, in the opinion of the investigator and/or Sponsor, places the subject at unnecessary risk through continued participation in the trial or does not allow the subject to adhere to the requirements of the protocol;
- The subject has a confirmed positive serum pregnancy test.

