8.2.3.1 Pharmacokinetics

Individual values will be listed for the PK parameters as shown below, and the following (non-model-based) descriptive statistics will also be provided: N (number of subjects with non-missing data), arithmetic mean, standard deviation, arithmetic percent CV (calculated as $100 \times$ standard deviation/arithmetic mean), median, minimum, maximum, geometric mean, and geometric percent CV (calculated as $100 \times \sqrt{\exp(s^2)} - 1$, where s^2 is the observed variance on the natural log-scale). On Day 10, the PK parameters are steady-state C_{avg} , AUC_{0-24hr} , C_{max} , C_{min} and T_{max} in subgroup 1. The frequency distribution with pre-specified exposure in two categories, <500 ng/mL and ≥ 500 ng/mL, for steady-state C_{avg} values on Day 10 in subgroup 1 will be tabulated. Descriptive statistics (mean and arithmetic percent

CV) will also be tabulated for trough plasma concentrations in both subgroups by study day for MK-5592. In addition, mean trough plasma concentrations in both subgroups will be plotted by study day.

A population PK model was developed in non-Chinese healthy volunteers and patients to characterize PK and its variability after POS IV administration. Data from this study will be added to the dataset and the effect of Chinese ethnicity on the pharmacokinetics of posaconazole will be assessed. Also the percentage of the population with $C_{avg} \geq 500$ ng/mL will be estimated using the population PK model. Other necessary pharmacokinetic parameters will also be estimated from the population PK models.

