8.2.3.3 Sample Size

The sample size for this study is based on overall objectives such as PK, safety and tolerability. Assuming a mean steady-state $C_{avg} = 1500$ ng/mL and a coefficient of variation (CV) = 35%, there is a greater than 90% probability that at least 18 out of 20 evaluable subjects enrolled in subgroup 1 will have a steady-state $C_{avg} \geq 500$ ng/mL. These calculations are based on the data of steady-state pharmacokinetics from 49 subjects enrolled in an earlier study of POS IV solution (P05520, [Table 5](#)). In order to have approximately 20 evaluable subjects in subgroup 1 and considering a potential dropout rate 30%, approximately 30 subjects will be enrolled in subgroup 1. The sample size for subgroup 2 is based on prior study experience and historical requirements for filing regarding the number of subjects that would need to constitute an adequate safety database for this formulation. Therefore, we will enroll approximately 30 subjects in subgroup 1 and 40 subjects in subgroup 2.

Table 5 PK Parameters Based on Previous Studies

Endpoint	Mean	CV	Source
C_{avg}	1500 ng/ml	0.35	MK-5592 PN05520 (n=49)
C_{max}	3280 ng/ml	0.74	
T_{max}	1.5 (0.98-4.0) ^a hr	-	

^a Median (minimum-maximum).

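### Per-protocol is the only set assigned to PK, so usable concentrations can be left out of the population PK model and its percentage with Cavg at or above 500 ng/mL

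*Combined protocol and SAP*

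**What the plan says.** Section 8.2.3 defines two analysis sets. All Subjects as Treated serves safety and tolerability. Of the per-protocol set it says "This population will be used for the PK analysis".

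Membership of the per-protocol set is described in general terms: "Compliance covers such considerations as exposure to treatment, availability of measurements and absence of major protocol deviations". There is no list of major deviations and no minimum number of doses or samples. Subjects who are compliant and "have available data from at least one treatment will be included in the primary analysis dataset". Exclusions may be of whole subjects or single values and are reported afterwards: "Any subjects or data values excluded from analysis will be identified, along with their reason for exclusion, in the CSR".

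Section 8.2.3.1 (Pharmacokinetics) holds two kinds of analysis. One is descriptive; its frequency table of Cavg below or at/above 500 ng/mL uses "values on Day 10 in subgroup 1 will be tabulated". The other is the population PK model, for which the text says "Data from this study will be added to the dataset and the effect of Chinese ethnicity on the pharmacokinetics of posaconazole will be assessed", without naming a set. The model then gives a second estimate of the percentage at or above 500 ng/mL. Estimating that percentage is part of the primary hypothesis statement in 3.1 and of 8.2.1.

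**The concern.** A per-protocol restriction suits a Day 10 non-compartmental summary, where a subject needs a full profile on a regular regimen. It suits a population PK model less well. The model takes each subject's actual dosing history and sample times, so irregular dosing or a short course makes a subject less informative, not unusable. Both subgroups have troughs scheduled on Days 3 and 6, before most subjects could be lost.

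Some events listed in 5.8 could also be judged major deviations: failing to comply with dosing, interrupting drug for more than three consecutive days, or needing a prohibited medication. Valid concentrations taken before such an event would go with the subject. At stake is whether one of the plan's two estimates of its primary percentage describes treated Chinese high-risk patients or only those judged compliant. That judgement has no fixed cut-off. Section 8.2.3 asks for deviations to be identified before unblinding, but the trial is open-label (5.2.3, 7.1.4.2).

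**Working it through.** **1. The plan's own figure.** Inputs from 8.2.3.3 and its Table 5: mean Cavg 1500 ng/mL, CV 35% (SD 525), threshold 500, at least 18 of 20.

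- Normal: z = (500 − 1500)/525 = −1.905, so p = 0.9716. Exact binomial P(at least 18 of 20) = 0.982.
- Lognormal: σ² = ln(1 + 0.35²) = 0.1156, σ = 0.340, μ = ln 1500 − 0.0578 = 7.255. Then z = (6.215 − 7.255)/0.340 = −3.06, so p = 0.9989 and the probability exceeds 0.9999.

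Both agree with the stated probability above 90%. Enrolment: 20/(1 − 0.30) = 28.6, or 29, against about 30 planned. The sample-size statement reproduces.

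**2. Room for bias at the planning values.** If p is the true share at or above 500, leaving subjects out cannot overstate it by more than 1 − p. That is 0.11 point under the lognormal and 2.8 points under the normal. The upper limit is reached only if every subject below 500 is excluded.

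**3. Range away from the planning values.** Let d be the share excluded, q the excluded subjects' rate at or above 500, and 0.972 the rate in the per-protocol set. The all-treated rate is (1 − d) × 0.972 + d × q. The documents give neither d nor q, so both are assumptions.

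| q | d = 10%: all-treated (difference) | d = 30%: all-treated (difference) |
|---|---|---|
| 1.00 | 97.4% (−0.3) | 98.0% (−0.9) |
| 0.97 | 97.1% (0.0) | 97.1% (0.0) |
| 0.90 | 96.4% (0.7) | 95.0% (2.1) |
| 0.80 | 95.4% (1.7) | 92.0% (5.1) |
| 0.70 | 94.4% (2.7) | 89.0% (8.1) |
| 0.50 | 92.4% (4.7) | 83.0% (14.1) |

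Differences are percentage points, per-protocol minus all-treated. The calculation treats the percentage as a simple share. The plan's estimate comes from a model pooled with earlier studies, and the bias in that estimate has not been computed.

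**4. Are the early troughs informative?** One-compartment superposition, with doses at 0, 12 and 24 h and then every 24 h (spacing as in 5.2.2), and half-life 30 h (4.2.2.1), so k = ln 2/30.

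- Steady-state trough, in units of one dose: e^(−24k)/(1 − e^(−24k)) = 0.574/0.426 = 1.349.
- Day 3, at 48 h: e^(−48k) + e^(−36k) + e^(−24k) = 0.330 + 0.435 + 0.574 = 1.339, or 99% of steady state. Day 6 gives 100%.
- Over half-lives of 20 to 66 h (range in the oral suspension circular, 12.10), Day 3 gives 118% to 59% and Day 6 gives 102% to 81%.

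These troughs carry information on clearance, but they are not an observed steady-state Cavg.

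**5. Who is affected.** A compliant subject stopped on Day 7 under 5.8 has data and meets the per-protocol wording. A subject without a Day 10 profile has no AUC over 24 h, hence no observed Cavg (4.2.3.1), under any set. What remains is the model, and in it the subjects judged non-compliant or short of measurements.

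**The case against.** The strongest reply is that 8.2.3.1 adds this study's data to the model without naming the per-protocol set, so the restriction is an inference. That is fair. But 8.2.3 assigns one set to PK, and the model sits under the Pharmacokinetics heading. If the text is instead read as silent, the set behind a primary percentage is undefined and the remedy is the same.

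A second reply is that exclusion of single values lets a deviator's good samples stay in. The text permits this but does not require it, and explaining exclusions in the study report is disclosure after the fact.

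Several stronger readings are tempting and do not stand:

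- A reader might infer from "A subject must be discontinued from the trial for any of the following reasons" that all early stoppers are lost. Following a mandated stop is not a deviation, and completion of therapy is not required.
- A reader might take "considering a potential dropout rate 30%, approximately 30 subjects will be enrolled in subgroup 1" to mean that 30% will be excluded. It is a dropout allowance to secure about 20 evaluable subjects in subgroup 1, not a forecast of per-protocol exclusions.
- A reader might infer that the low-exposure tail is what goes missing. Section 4.1.1 reports no association of high concentrations with adverse experiences, and 12.10 none between liver-test elevations and higher concentrations. Invasive fungal infection could plausibly track low exposure, but it is a mandated stop. In the oral-suspension AML/MDS trial in 12.10, proven or probable cases on therapy plus 7 days were 7 of 304 (2%).

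**Conclusion.** The point holds in a limited form. The plan gives PK one analysis set, with membership left to judgement, and on a plain reading applies it to a model that does not need it. Valid concentrations from subjects judged to have major deviations, or removed for lack of measurements, can be left out of the model-based percentage.

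The documents do not show that this percentage is biased, nor in which direction. At the planning values the effect is negligible under a lognormal Cavg. The 0 to 14 point range at 30% excluded rests on assumed exclusion shares and assumed rates among those excluded; a rate above 97% reverses the sign. The case for change is that usable data are kept and open-label judgement is removed from a primary estimate. It is a cheap improvement, not a defect that undermines the trial.

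**What to change.** In 8.2.3, add a population PK set: all treated subjects with at least one quantifiable post-dose concentration and recorded dose and sample times. Exclude single invalid values by rules fixed before concentrations are released, in place of the reference to unblinding. In 8.2.3.1, name this set for the model and for the model-based percentage at or above 500 ng/mL. Keep the per-protocol set for the Day 10 non-compartmental tables and as a sensitivity run of the model. List the major deviations that remove a subject from it.

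The cost is SAP wording and one extra model run. Predictions for subjects with only one or two troughs will be less precise. The observed Day 10 table does not change.
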